8 OBJECTIVES AND ENDPOINTS

Table 2. Objectives and Endpoints

	Objective	Endpoint	Analysis
Primary	Determine the MTD of a single IV infusion of EGFRvIII CAR T cells in patients with newly-diagnosed WHO Grade IV malignant glioma.	MTD	See Section 15.4
Key Secondary	To determine the DLT of a single IV infusion EGFRvIII CAR T cells in patients with newly-diagnosed WHO Grade IV malignant glioma.	DLT	See Section 15.5
Exploratory	To determine if EGFRvIII CARs transferred into patients with WHO Grade IV malignant glioma expand.	Median number of EGFRvIII CARs in peripheral blood and KI67	See Section 15.6
Exploratory	To determine if EGFRvIII CARs persist and remain functional in the periphery.	Median number of EGFRvIII CARs by tetramer and functional assays	See Section 15.6

Exploratory	To assess whether EGFRvIII CARs traffic to tumor site.	Median proportion of injected ¹¹¹ In-labeled EGFRvIII CARs present in tumor	See Section 15.6
Exploratory	To describe the survival experience of patients treated with EGFRvIII CAR T cells.	Median survival	See Section 15.6
Exploratory	To describe the progression-free survival experience of newly-diagnosed, EGFRvIII-expressing WHO Grade IV malignant glioma patients treated with EGFRvIII CAR T cells.	Proportion of patients alive without disease progression 6 months after EGFRvIII CAR treatment	See Section 15.6

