Adverse Events									Ongoing		
Con Meds									Ongoing		

¹ Some patients may not receive DI TMZ cycle 3 or cycles 2 and 3, please see Section 9.1 for details about DI TMZ requirements.

² 48 hours (+72 hours) after last dose of DI TMZ

³ ± 7 days from the last dose of TMZ

⁴ Within 2 days prior to CAR T Cell infusion.

⁵ Prior to Cycle 4 and then prior to every other Cycle (Cycle 6, 8, etc), at the discretion of the treating physician.

⁶ Day 14 (± 3 Days) of the TMZ cycle.

⁷ Day 21 (± 3 days) and day 28 (± 7 days) of each 5-day TMZ cycle

⁸ Day 28 (± 7 days) of each 5-day TMZ cycle

⁹ Prior to CAR T Cell Infusion, and at 1 and 4 hours and days 1, 2, 5, and 10 post CAR T Cell infusion. Draw 1 red top and 1 purple top (3 mL each) and 1 gold top at each time point.

¹⁰ 28 days post CAR T Cell Infusion. Draw 1 red top and 1 purple top (3mL each) and 1 gold top.

¹¹ 2 red tops (10 mL each).

¹² Prior to CAR T Cell Infusion on day 22 (+3 day window), and at 1, 5, and 10 days after the infusion (9 yellow tops (8.5mL each) and 1 red top (10mL) at each time point.

¹³ 1, 3, 6, and 12 months post CAR T Cell infusion and then yearly and at progression. Draw 9 yellow tops (8.5mL each) and 1 red top (10mL) at each time point. Draws will coincide with standard of care return clinic visits.

¹⁴ At least 48 hours after last dose of DI TMZ. Patients will be pre-medicated 30-60 minutes prior to infusion with acetaminophen (650 mg po) and Benadryl (25 mg by mouth) to reduce infusion-related reactions. Patients must be on stable of decreasing steroid dose (≤ 4 mg/day) 2 weeks prior to CAR T cell infusion.

¹⁵ Days 1-21 of a 28-day cycle, at the discretion of the treating physician.

¹⁶ 5 day TMZ to be taken on days 1-5 of a 28 day cycle. The first cycle of 5-day TMZ will be initiated approximately 1 month after CAR T Cell infusion.

¹⁷ Vital signs will be measured prior to the CAR T cell infusion and every 15 minutes for 1 hour post-infusion. Measurements to be reported include temperature in Celsius or Fahrenheit, pulse (beats per minute), respiratory rate (breaths per minute) and blood pressure.

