12.5 Follow-up Period

Following the infusion, blood samples for IM (9 yellow, 1 red) will be drawn 1, 5, 10, and 28 days after the infusion, then 3 and 6 months, then yearly until progression (or death or lost to contact). Lymphocytes in patients' peripheral blood will be analyzed by FACS and quantified for persistence. Isolated PBMCs will be stained with fluorescence-labeled antibodies against cell surface and intracellular cytokine markers to determine function including staining with our novel EGFRvIII tetramer reagent. Whole planar imaging, followed by SPECT/CT, if appropriate, will be done on days 1, 2, and 3 following infusions to determine the IC localization of ¹¹¹In-labeled EGFRvIII CARs. Quantification of radioactivity will be assessed by previously published methods that calculate counts from reconstructed images based on the percentage of injected dose. Blood will be taken for RCR PCR at 3, 6 and 12 months and blood for evaluation of CRS (1 red, 1 purple top – 3mLs each) will be drawn pre-infusion, 1 and 4 hours after CARs infusion, and on days 1, 2, 5, 10, and 28.

Patients treated with EGFRvIII CARs will be followed for survival and data recorded by the study coordinator/research nurse until death or for 15 years (whichever comes first).

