Two sets of efficacy analyses will be conducted. One set of analysis will focus on all patients who enroll in the study whether or not EGFRvIII CAR treatment is administered, and the other set of analyses will focus on patients who receive EGFRvIII CAR treatment. Among all patients, Kaplan-Meier methods will graphically describe their survival from the time of study enrollment or histologic diagnosis. Among patients who receive CAR treatment, Kaplan-Meier methods will also be used to describe the distribution of overall survival and progression-free survival. In these analyses, OS and PFS will be computed from the date that CAR treatment was initiated. OS is defined as the time between the landmark (e.g. histologic diagnosis or initiation of CAR treatment) and death or date of last follow-up. PFS is defined as the time between the landmark and first progression, death, or last follow-up if the patient remains alive without disease progression.

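### Section 15.6 censors PFS at last follow-up, not last disease assessment, so time with unknown tumour status can count as progression-free

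*Combined protocol and SAP*

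**What the plan says.** The only PFS censoring rule is in Section 15.6: "PFS is defined as the time between the landmark and first progression, death, or last follow-up if the patient remains alive without disease progression". The sentence before it reads "OS is defined as the time between the landmark (e.g. histologic diagnosis or initiation of CAR treatment) and death or date of last follow-up", so OS and PFS share one censoring term. For patients who receive CAR treatment, "Kaplan-Meier methods will also be used to describe the distribution of overall survival and progression-free survival", counted from the start of that treatment. Table 2 (Section 8) gives the PFS endpoint as "Proportion of patients alive without disease progression 6 months after EGFRvIII CAR treatment".

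The surrounding text sets out two kinds of follow-up:

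- **Imaging.** Table 6 places post-infusion MRI in the column for 5-day TMZ Cycles 4-12. Footnote 5 times it as "Prior to Cycle 4 and then prior to every other Cycle (Cycle 6, 8, etc), at the discretion of the treating physician".
- **Survival.** Section 12.5 says "Patients treated with EGFRvIII CARs will be followed for survival and data recorded by the study coordinator/research nurse until death or for 15 years".
- **After leaving the study.** Section 12.6 says radiographic response will be followed as well as survival and later therapies, but gives no schedule.
- **After withdrawal.** For infused patients who are withdrawn, Section 12.7.2 requires survival follow-up and makes radiographic results from later regimens optional.

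No section says which contact or assessment fixes the PFS censoring date, or how missed assessments are treated.

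**The concern.** Being alive can be established by a telephone call. Being free of progression requires someone to have looked. If the PFS clock runs to the last follow-up of any kind, a patient whose assessments have stopped stays in the risk set as progression-free until last contact, or until a death that is then dated long after the unseen progression. Both push the curve up.

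The effect is largest late in the curve, where scheduled imaging has ended and few patients remain. That part would be read as durable benefit. With about 18 patients at the MTD (Section 15.7), a few extended times can move the estimate visibly.

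**Working it through.** The documents state no expected PFS, event count or rate of stopped assessments, so there is no plan figure to reproduce. Everything below illustrates the rule under stated assumptions.

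**Scheduled imaging window.** The first 5-day cycle starts about 28 days after infusion and cycles last 28 days. Scans before Cycles 4, 6, 8, 10 and 12 therefore fall near days 28, 84, 140, 196 and 252, which is every 56 days. Survival contact may run to 15 years.

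**Example by hand, 18 patients (invented data).** Nine have documented progression at 1, 1.5, 2.5, 3, 3.5, 4.5, 5, 5 and 5.5 months. Three stop scans at 2, 3.1 and 4 months and are known alive at 12 months. Six are scanned progression-free to 12 months.

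- Written rule: nobody is censored before 12 months, so 6-month PFS = 9/18 = 50.0%. The median is 5.5 months.
- Censored at last assessment: 16/18 × 13/15 × 11/12 × 6/10 = 42.4%. The median is 5.0 months.
- Difference: 50.0 − 42.4 = 7.6 points.

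**Average effect, by simulation (600,000 patients per setting).** Assumptions:

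- exponential time to progression;
- median 8 months from progression to death;
- a scan every 56 days from day 28, except that 10%, 20% or 30% of patients stop at a time uniform over months 1 to 12;
- contact to 24 months for everyone.

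Excess is the written rule minus the estimate with all patients scanned throughout.

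| True median PFS (months) | Share stopping | True 12-month PFS | All scanned | Written rule | Excess at 12 months (points) | Excess at 6 months (points) |
|---|---|---|---|---|---|---|
| 6 | 10% | 0.250 | 0.252 | 0.273 | 2.1 | 0.6 |
| 6 | 20% | 0.250 | 0.251 | 0.292 | 4.1 | 1.1 |
| 6 | 30% | 0.250 | 0.252 | 0.313 | 6.1 | 1.7 |
| 9 | 10% | 0.397 | 0.398 | 0.416 | 1.9 | 0.4 |
| 9 | 20% | 0.397 | 0.398 | 0.435 | 3.7 | 0.8 |
| 9 | 30% | 0.397 | 0.399 | 0.456 | 5.7 | 1.3 |
| 12 | 10% | 0.500 | 0.501 | 0.517 | 1.6 | 0.3 |
| 12 | 20% | 0.500 | 0.501 | 0.534 | 3.3 | 0.7 |
| 12 | 30% | 0.500 | 0.503 | 0.552 | 5.0 | 1.0 |

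Censoring at last assessment, with deaths after stopping also censored there, came within about 0.1 point of the all-scanned estimate at both times, and so within 0.5 point of truth at 12 months. At 6 months all estimates also carry the delay from the 56-day scan interval, which no censoring rule removes.

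**Sensitivity to the assumptions.**

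- If progression is recorded when it occurs rather than at the next scan, the excess is 1.3 to 5.4 points at 12 months and 0.4 to 2.1 at 6 months.
- If all the stopping falls in months 1 to 6 (true medians 4, 6 and 10 months, n = 18), the 6-month excess is about 1 to 5 points.
- If deaths after stopping still count as events while survivors are censored at last assessment, 12-month PFS is 0.257 to 0.273 against 0.250 (median 6 months) and 0.501 to 0.507 against 0.500 (median 12 months). That is a partial correction only, so late deaths need their own rule.

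**The case against.** Four points deserve weight.

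1. PFS is the last-listed exploratory objective and is only described. Section 12.1 says that detecting tumour response is not the study's purpose. This stands and limits the consequence.
2. Disease assessment is not confined to five MRIs. Section 12.1 allows progression to be called on neurologic decline whatever the MRI shows, Section 12.8.2 has examinations at each visit, and immune-monitoring visits continue until progression alongside standard care. This stands as a reason why the bias may be small in practice. It does not give the censoring date.
3. A reader might infer that withdrawn patients are followed for survival only. Sections 12.6 and 12.7.2 do not support that: radiographic follow-up is foreseen, though unscheduled in one and optional in the other.
4. The condition that the patient remains alive without progression could be read as requiring known status. The text does not say as of which assessment, so two analysts could draw different curves from the same data.

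A reader might also infer a much larger bias by assuming that nobody is assessed after day 252. Twelve-month PFS under the written rule is then 0.36, 0.51 and 0.60 against a true 0.25, 0.40 and 0.50 (medians of 6, 9 and 12 months), or 10 to 11 points too high. The documents do not support that assumption, for the reasons in point 2. Nor does the number measure the censoring rule. In that setting, moving survivors' censoring to last assessment while counting later deaths gives 0.34, 0.47 and 0.56, only 2 to 4 points lower. Censoring everyone without documented progression at day 252 leaves nobody at risk, so 12-month PFS cannot be estimated. At 6 months the two rules agree exactly (0.58, 0.70 and 0.76).

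**Conclusion.** The concern holds as a moderate defect in an exploratory analysis. Section 15.6 gives PFS the OS censoring term, while assessment and contact can diverge for years, so following the text counts unassessed time as progression-free. The bias is upward.

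Its size depends on a quantity the documents do not give. With 10% to 30% of patients stopping scans in months 1 to 12 but still contacted, true median PFS of 6 to 12 months and a median of 8 months from progression to death, 12-month PFS is about 2 to 6 points too high and 6-month PFS about 0.5 to 2 points. If few patients stop, or standard-care assessments continue, it is smaller. The 6-month proportion in Table 2 is affected only by patients whose assessments stop before 6 months. The MTD, the DLT analysis and the sample size are unaffected.

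**What to change.** In Section 15.6:

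- Censor PFS at the date of the last adequate disease assessment (MRI or clinical/neurologic evaluation) that shows no progression.
- State that a death or progression after two or more missed assessments is censored at that date, with a sensitivity analysis counting it as an event. Table 6 ends at Cycle 12, so name the interval used to count missed assessments after that.
- Keep last contact as the censoring date for OS only.

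The edit is a few sentences and adds no study procedure, but the date of each assessment used must be in the database. PFS may look slightly less favourable, and fewer patients remain at risk in the tail. The new rule is unbiased only if stopping assessments is unrelated to progression; the sensitivity analysis shows how far the result depends on that.

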15.7 Sample Size Calculation

After completion of the expansion cohort, we anticipate that 18 patients (6 without ¹¹¹In-labeled EGFRvIII CARs and 12 with) will have been treated at the MTD. One motivation for treating additional patients at the MTD is to more precisely estimate the rate of DLT at the MTD. Tabulated below as a function of the DLT rate is the half width of the associated 95% confidence interval:

Table 7. Half Width of 95% Confidence Interval as a Function of the DLT Rate

DLT Rate	Half Width of 95% Confidence Interval
0.05	0.025
0.1	0.032
0.15	0.039
0.2	0.044
0.25	0.047

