9.1.1 Dose Escalation and Expansion

A classical “3+3” study design will be used to estimate the MTD for CAR-specific T cells treatment among patients with newly-diagnosed WHO grade IV malignant glioma. As shown below in [Table 3](#), 4 dose levels will be considered based on transduced cells/kg: #1: 4.5 x 10⁶/kg, #2: 1.5 x 10⁷/kg, #3: 4.5 x 10⁷/kg, and #4: 1.5 x 10⁸/kg.

Table 3. Dose Escalation and Expansion

Dose Escalation and Expansion			
Cohort	Dose of CAR-specific T cells	# of Subjects	Schema
1	4.5 x 10 ⁶ /kg	3-6	Dose escalation: “Standard 3+3”
2	1.5 x 10 ⁷ /kg	3-6	
3	4.5 x 10 ⁷ /kg	3-6	
4	1.5 x 10 ⁸ /kg *	3-6	
* If the patient’s targeted dose is 1.5 x 10 ⁸ /kg (dose level #4), the calculated dose will be capped at 1.0 x 10 ¹⁰ total cells.			

Starting with the lowest dose level, cohorts of 3-6 subjects will be accrued at each dose level according to the following dose escalation rules:

Table 4. Dose Escalation Rules

Number of patients with DLT observed during the first 4 weeks after CAR treatment	Escalation Decision Rule
0 out of 3	Enter 3 patients at the next dose level
1 out of 3	Enter 3 more patients at this dose level. 
 If 0 of these 3 patients experience DLT, proceed to the next dose level If 1 or more of this group suffer DLT, then dose escalation is stopped. Three (3) additional patients will be entered at the next lowest dose level if only 3 patients were treated previously at that dose.

≥ 2	Dose escalation will be stopped. Three (3) additional patients will be entered at the next lowest dose level if only 3 patients were treated previously at that dose.
DLT = dose limiting toxicity; MTD = maximum tolerated dose	

If a patient terminates the infusion of EGFRvIII CAR T cells prematurely or is lost to follow-up during the first 4 weeks after CAR treatment without experiencing a DLT, then the patient will not be evaluable for the determination of the MTD and will be replaced. The MTD is the highest dose level at which ≤ 1 of 6 patients experiences DLT during the 4 week observation period after CAR treatment. The last patient in a given cohort, receiving that dose level, should be observed for DLTs for at least 4 weeks prior to moving on to the next cohort/higher dose. Section 9.1.2 provides information about what constitutes a DLT.

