An expanded cohort of a total of 12 patients will be enrolled at the MTD of EGFRvIII CAR T cells in order to obtain a more precise estimate of the probability of unacceptable toxicity. This cohort will also have the cells radiolabeled with ^{111}In to track their distribution. Briefly, CARs will be counted and re-suspended in PBS. $4\text{-}6 \times 10^8$ cells will be labeled with 500 micro Ci of ^{111}In . The cells will be washed and mixed with cold CARs to achieve the desired cell dose with a total of 500 μCi of ^{111}In . The labeled CARs will be infused into the patient through an intravenous catheter within the Ambulatory Bone Marrow Transplant (BMT) Unit. Distribution of ^{111}In -labeled EGFRvIII CARs will be evaluated at 1, 2, and 3 days post-infusion using whole body planar imaging followed by SPECT/CT, when indicated.

In the rare event that a sufficient amount of CAR-specific T cells cannot be generated for a patient's intended dose within the dose-escalation portion of this study, the patient will be treated at a lower pre-defined dose level using available CAR-specific T cells. If this patient experiences a DLT, data will be carefully reviewed to determine its impact upon dose escalation and future patient treatment. If this situation occurs with the expanded cohort, all available cells will be administered.

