15.5 Secondary Objectives

To determine the DLT of a single IV infusion EGFRvIII CAR T cells in patients with newly-diagnosed WHO grade IV malignant glioma. The proportion of patients who experience DLT within each dose level will be tabulated.

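### The DLT rate at the MTD would combine 6 patients retained because their dose level had at most 1 DLT with 12 later patients, which biases it modestly low; show the 12 separately as well

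*Combined protocol and SAP*

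**What the plan says.** Section 9.1.1 sets the selection rule: "The MTD is the highest dose level at which ≤ 1 of 6 patients experiences DLT". When escalation stops, the level below is filled up: "additional patients will be entered at the next lowest dose level if only 3 patients were treated previously at that dose".

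The expansion comes after the MTD has been chosen: "An expanded cohort of a total of 12 patients will be enrolled at the MTD of EGFRvIII CAR T cells", and its purpose is given as "in order to obtain a more precise estimate of the probability of unacceptable toxicity".

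Section 15.7 then states "After completion of the expansion cohort, we anticipate that 18 patients" will have been treated at the MTD, made up of 6 without and 12 with the radiolabel. It adds: "One motivation for treating additional patients at the MTD is to more precisely estimate the rate of DLT at the MTD". It gives planning half widths ("Table 7. Half Width of 95% Confidence Interval as a Function of the DLT Rate"). Section 15.5 describes the analysis of the secondary objective: "The proportion of patients who experience DLT within each dose level will be tabulated".

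Neither section says that the 6 and the 12 will be combined. However, a proportion per dose level, with 18 patients expected at the MTD, places all 18 in one cell. Nothing in section 15 separates the two groups, adjusts for the selection or mentions it.

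**The concern.** The two groups reach the MTD cell by different routes. The 12 expansion patients are enrolled after the level has been chosen, so their DLT outcomes play no part in choosing it. The 6 escalation patients are counted at the MTD only because 0 or 1 of them had a DLT; with 2 or more, the level would not have been the MTD. On average they therefore look safer than the dose really is, and they make up a third of the sample.

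A better estimate of toxicity at the MTD is the safety reason given for the expansion, and DLT is the key secondary endpoint in Table 2. An unlabelled 18-patient rate leans toward the safer side, and a reader of the report could not tell that part of the sample had been screened for low toxicity.

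**Working it through.** **Inputs.** Selection rule of at most 1 DLT in 6, and filling of the lower level to 6 (section 9.1.1 and Table 4); 12 expansion patients (section 9.1.1); 18 in total, 95% level and DLT rates of 0.05 to 0.25 (section 15.7 and Table 7).

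**The plan's own figure.** Table 7 prints half widths of 0.025, 0.032, 0.039, 0.044 and 0.047. They do not reproduce with 18 patients. The Wald half width 1.96 × √(p(1−p)/18) is 0.101, 0.139, 0.165, 0.185 and 0.200, about four times the printed values. The printed values are close to 1.96 × √(p(1−p))/18 = 0.024, 0.033, 0.039, 0.044 and 0.047, which suggests division by 18 where √18 was needed. That is a separate and larger problem. The recomputed half widths are the yardstick here.

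**Step 1: the 6 selected patients.** A level can be filled to 6 and pass in two ways: 1 of 3 and then 0 of 3, or 0 of 3 and, after a step down, at most 1 of the next 3. Together these are exactly the outcomes with X ≤ 1 in 6. What happened at other levels does not depend on these outcomes. With q = 1−p:

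E[X | X ≤ 1] = 6pq⁵ / (q⁶ + 6pq⁵) = 6p / (q + 6p) = 6p / (1 + 5p).

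The expected rate in the 6 is p/(1+5p), which is below p for every p between 0 and 1.

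**Step 2: the 18 together.**

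Expected rate = [6p/(1+5p) + 12p] / 18, so bias = −5p² / [3(1+5p)].

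At p = 0.20: (6 × 0.10 + 12 × 0.20)/18 = 3.0/18 = 0.167, a bias of −0.033.

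| True rate p | Expected rate, 6 | Expected rate, 18 | Bias | Relative | Wald half width, n=18 |
|---|---|---|---|---|---|
| 0.05 | 0.040 | 0.047 | −0.003 | −7% | 0.101 |
| 0.10 | 0.067 | 0.089 | −0.011 | −11% | 0.139 |
| 0.15 | 0.086 | 0.129 | −0.021 | −14% | 0.165 |
| 0.20 | 0.100 | 0.167 | −0.033 | −17% | 0.185 |
| 0.25 | 0.111 | 0.204 | −0.046 | −19% | 0.200 |

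**Step 3: simulation check.** The full four-level 3+3 plus 12 expansion patients was simulated with 60,000 trials for each of three assumed dose-toxicity curves, with the top level filled to 6. At a level with true rate 0.20 it gave about 0.10 in the 6, 0.167 in the 18 and 0.20 in the 12. Averaged over the chosen level, the 18-patient rate against the true rate was 0.155 against 0.187, 0.128 against 0.151, and 0.171 against 0.208.

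**Step 4: interval and accuracy, by enumerating 6 selected plus 12 ordinary outcomes.**

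| True rate p | Coverage, exact 95% CI on 18 | Chance CI lies wholly below p (without selection) | RMSE, 18 | RMSE, 12 alone |
|---|---|---|---|---|
| 0.05 | 99.4% | 0 (0) | 0.048 | 0.063 |
| 0.10 | 99.8% | 0 (0) | 0.065 | 0.087 |
| 0.15 | 99.7% | 0 (0) | 0.077 | 0.103 |
| 0.20 | 97.0% | 2.8% (1.8%) | 0.088 | 0.115 |
| 0.25 | 98.7% | 1.1% (0.6%) | 0.099 | 0.125 |

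**The case against.** **Pooling is implied, not written.** Section 15.7 is a planning statement that names no final estimator or interval method, and the table in section 15.5 is descriptive. No test, threshold or decision uses the 18-patient rate. This stands, and it limits the point to how the rate is reported.

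**The 18-patient rate is the more accurate one.** Its RMSE is lower at every rate in Table 7 despite the bias. Using all 18 is a defensible trade of bias for variance, in keeping with the stated aim of precision. This also stands, so the 12-patient rate should not replace it.

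**The 12 are not a perfect reference.** They receive radiolabelled product, and section 9.1.1 lets an expansion patient receive all available cells when the full dose cannot be made. Their rate is free of selection on DLT outcome, but it may not describe the full MTD dose. This stands and belongs in the report.

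**A stronger reading is tempting:** that the confidence interval would also mislead. The calculations do not support this over the rates the plan considers, where exact coverage is about 97% or more and the chance of lying wholly below the truth stays near or under the nominal 2.5%. Beyond Table 7 the effect is irregular: that chance is 3.4%, 6.8% and 3.2% at assumed rates of 0.30, 0.35 and 0.40 (1.4%, 2.4% and 0.8% without selection), and coverage at 0.35 is 93.1%. A level with those rates passes the rule of at most 1 in 6 with probability 0.42, 0.32 and 0.23. That does not justify a general claim of interval failure.

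**Conclusion.** The point holds as a modest reporting matter. The downward direction is certain if the 6 and 12 are combined. The size is 0.003 to 0.046 over true rates of 0.05 to 0.25, which is small at the low end and up to about a quarter of the recomputed half width at 0.25 (0.046/0.200 = 0.23). It grows with the true rate, so it is largest when a more toxic level has passed by chance.

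The documents do not support a reader's inference that the plan commits to a formal binomial analysis of the 18, that its exact interval is invalid, or that the 12 alone give the better single estimate.

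The figures assume that section 15.5 is applied as written to all patients at the MTD, that the level was filled to 6, and that patients at a level share one DLT probability. Table 4 does not say what follows 0 of 3 at level 4. If only 3 were treated there before the expansion, the expected rate on 15 would be 12p/15 = 0.8p, also low.

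**What to change.** In section 15.5, tabulate two DLT rates at the MTD: the 12 expansion patients with a Clopper-Pearson 95% interval, and the 18 patients together, labelled as including 6 selected by the 3+3 rule. Say in section 15.7 that the second rate is expected to be somewhat low for that reason. List the cell doses that the expansion patients actually received, and note that their rate is free of selection on DLT outcome only. Specify this before the DLT data are known.

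The cost is one table row and a footnote, with no extra patients or visits. The expansion-only interval is wider: the Wald half width at a rate of 0.20 is 0.226 with 12 patients against 0.185 with 18, and the exact half width at an observed rate of one in six is 0.232 (2 of 12) against 0.189 (3 of 18).

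### Table 7's 95% confidence interval half widths for the DLT rate at the MTD are about four times too small for the planned 18 patients

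*Combined protocol and SAP*

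**What the plan says.** Section 15.7 of the combined protocol and SAP states "we anticipate that 18 patients" treated at the MTD once the expansion is complete: 6 with unlabeled cells and 12 with ¹¹¹In-labeled cells. It gives a reason for the added patients: "One motivation for treating additional patients at the MTD is to more precisely estimate the rate of DLT at the MTD". Table 7 follows, introduced by "Tabulated below as a function of the DLT rate is the half width of the associated 95% confidence interval". Its five rows are:

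| DLT rate | Stated half width |
|---|---|
| 0.05 | 0.025 |
| 0.10 | 0.032 |
| 0.15 | 0.039 |
| 0.20 | 0.044 |
| 0.25 | 0.047 |

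Neither the formula nor the interval method is named. Section 9.1.1 gives the 12-patient expansion the same purpose, without a figure: "in order to obtain a more precise estimate of the probability of unacceptable toxicity". It also says the cells in this cohort will be radiolabeled "to track their distribution".

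**The concern.** A half width of 0.047 at a DLT rate of 0.25 means the rate would be known to within about 5 percentage points. Eighteen binary observations cannot give that: one patient more or fewer with a DLT moves the observed proportion by 1/18, or 5.6 points, which is more than any half width in the table.

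Table 7 is the only numerical content of the sample size section beyond the patient count, and no other figure for precision or power appears in the document. A reader of the protocol, including the IRB and the Cancer Protocol Committee that must review it under section 16.2, would conclude that the expansion pins down the toxicity rate of a gene-modified cell product far more tightly than it will.

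**Working it through.** **Inputs.** From section 15.7: n = 18 at the MTD, 95% confidence, and the DLT rates p and stated half widths h of Table 7. A half width implies a two-sided interval, so z = 1.96.

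**Step 1: try to reproduce the table.** The Wald half width is 1.96 × √(p(1−p)/18). At p = 0.25 this is 1.96 × √(0.1875/18) = 1.96 × 0.1021 = 0.200. For all rows:

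| p | Stated h | Wald, n = 18 | Ratio to stated | Wald interval |
|---|---|---|---|---|
| 0.05 | 0.025 | 0.101 | 4.03 | −0.051 to 0.151 |
| 0.10 | 0.032 | 0.139 | 4.33 | −0.039 to 0.239 |
| 0.15 | 0.039 | 0.165 | 4.23 | −0.015 to 0.315 |
| 0.20 | 0.044 | 0.185 | 4.20 | 0.015 to 0.385 |
| 0.25 | 0.047 | 0.200 | 4.26 | 0.050 to 0.450 |

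The table is not reproduced. The lower Wald limit is negative in the first three rows, so a symmetric half width is a poor summary at this sample size.

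**Step 2: try other methods at n = 18.** The results, over p = 0.05 to 0.25, are:

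- Wilson: 0.121 to 0.187.
- Clopper-Pearson, evaluated at x = 18p: 0.132 to 0.213, about 4.5 to 5.3 times the stated values.
- Agresti-Coull: 0.141 to 0.191.
- Wald with continuity correction: 0.129 to 0.228.
- One-sided z of 1.645: 0.085 to 0.168.
- The standard error alone: 0.051 to 0.102, still about twice the stated values.

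None of these gives the table.

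**Step 3: try other sample sizes.** Counting only the 12 expansion patients gives Wald half widths of 0.123 to 0.245, which is further away. Doubling n to 36 gives 0.071 to 0.141, still about three times the stated values. Solving for the n that the table implies, n = p(1−p)(1.96/h)², gives 292, 338, 322, 318 and 326. Alternatively, holding n at 18 and solving for the confidence level gives about 35% to 37% instead of 95%.

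**Step 4: look for a likely cause.** The implied n clusters near 18² = 324, which suggests that the standard deviation was divided by n and not by √n. Testing that, 1.96 × √(p(1−p))/18 gives:

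| p | Divided by 18 | Stated h |
|---|---|---|
| 0.05 | 0.0237 | 0.025 |
| 0.10 | 0.0327 | 0.032 |
| 0.15 | 0.0389 | 0.039 |
| 0.20 | 0.0436 | 0.044 |
| 0.25 | 0.0472 | 0.047 |

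Three rows agree to three decimals. The other two differ by 0.0013 and 0.0007.

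**Step 5: what 18 patients do provide.** Exact (Clopper-Pearson) 95% limits by observed count:

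| DLTs / 18 | Estimate | Exact 95% limits | Half width | Upper limit minus estimate |
|---|---|---|---|---|
| 0 | 0% | 0 to 18.5% | 0.093 | 18.5 points |
| 1 | 5.6% | 0.1 to 27.3% | 0.136 | 21.7 points |
| 2 | 11.1% | 1.4 to 34.7% | 0.167 | 23.6 points |
| 3 | 16.7% | 3.6 to 41.4% | 0.189 | 24.8 points |
| 4 | 22.2% | 6.4 to 47.6% | 0.206 | 25.4 points |
| 5 | 27.8% | 9.7 to 53.5% | 0.219 | 25.7 points |
| 6 | 33.3% | 13.3 to 59.0% | 0.228 | 25.7 points |

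**The case against.** The arithmetic itself has no rebuttal. The fair objections concern how much depends on it.

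- **Precision is one reason among others.** Section 15.7 calls it one motivation, and the same 12 patients serve the ¹¹¹In trafficking objective. This stands: the error does not remove every reason for the cohort.
- **No decision rule uses Table 7.** The MTD is set by DLT counts under sections 9.1.1 and 15.4, the expansion has no toxicity threshold tied to these half widths, and section 15.5 only tabulates the proportion with DLT at each dose level. This also stands. Patient numbers, escalation and the primary endpoint are unaffected, and the plan never claims to test an acceptable rate against an unacceptable one.
- **The qualitative claim remains true.** Eighteen patients do estimate the rate better than six: at a DLT rate of 0.20 the Wald half width falls from 0.320 to 0.185. The direction is right and the size is wrong.
- **The cause is a guess.** The document gives no formula and two rows do not match exactly, so division by n is an inference. The discrepancy does not depend on it.
- **A plus-or-minus restatement has its own weakness.** Saying ±10 to ±20 points is about right for half widths, but the exact interval is asymmetric: from 1 to 6 DLTs in 18, its upper limit lies 22 to 26 points above the estimate. A corrected sentence should say so.

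**Conclusion.** Table 7 is wrong as written. For the 18 patients the plan states, its half widths are too small by a factor of 4.0 to 4.3 on the Wald formula, and by more on exact methods. At a DLT rate of 0.25 the design gives about ±20 points where the table says about ±5. The tabulated precision corresponds to roughly 290 to 340 patients at the MTD.

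The Wald comparison assumes a two-sided 95% interval and all 18 patients evaluable for DLT at a common rate. Fewer evaluable patients would make the true precision worse. Because this is the only quantified precision claim in the document and it concerns toxicity, it must be corrected, even though no dosing or escalation rule depends on it.

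**What to change.** 1. Replace Table 7 with values for n = 18. The better form is the exact 95% limits for 0 to 6 DLTs out of 18, as tabulated in the check. If a table indexed by DLT rate is kept, the Wald half widths are 0.101, 0.139, 0.165, 0.185 and 0.200, with a note that the interval crosses zero at rates of 0.05, 0.10 and 0.15.
2. Restate the precision in section 15.7: the half width is roughly 10 to 20 percentage points over the range of rates considered, and with exact limits the upper bound can lie about 25 points above the observed rate.
3. Name the interval method in 15.7 and use the same one when the DLT rate at the MTD is reported. Clopper-Pearson is a reasonable choice with small counts; Wilson would also be defensible.

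The cost is one table and a sentence or two, submitted as an amendment. It needs no extra patients and no change to conduct. The stated precision becomes less favourable, and the rationale for the expansion then rests on a modest gain over six patients together with the trafficking objective.
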